## 4.2.8 Analyses of Safety

All safety variables will be summarized for patients in the SP using descriptive statistical methods stratified by treatment regimen and cirrhosis status and overall.

An overview of tables for the individual values is given in Table 12.

The layouts of the tables mentioned above are provided in Part II of the SAP (Table Shells).

## 4.2.8.1 Exposure to Study Medication

One table will show the frequencies for early discontinuation and exceedance of Abbvie Regimen or Ribavirin and the corresponding reasons for SP by treatment regimen and cirrhosis status. The Abbvie Regimen is considered to have been prematurely discontinued if actual duration is shortened for more than 7 days. The duration for taking Abbvie regimen is considered to have been exceeded if the actual duration is prolonged for more than 7 days. Furthermore, summary statistics will be generated for the duration of ABBVIE regimen taken and the duration of ribavirin taken, i.e. n, mean, median, standard deviation [SD], minimum, maximum.

Unintended medication errors, i.e. patient missed taking Paritaprevir/r-Ombitasvir or Dasabuvir for at least 7 days in a row, will be displayed by medication for the entire treatment period.

#### 4.2.8.2 Co-medication

Treatments, surgical and medical procedures will be coded by AbbVie assigning appropriate preferred and class terms. Frequencies will be displayed for SP by treatment regimen and cirrhosis status.

In one table, the co-medication (preferred term) will be grouped by class. Only co-medication received during treatment specified by ABBVIE regimen will be displayed (Treatment profiles: A1, A2, C1 Drug B, C2 Drug B, C3 Drug B, D).

In another table, the co-medication (preferred term) will be grouped by profile. All treatment profiles will be considered, i.e.:

- A1: Continued (A1)
- A2: Permanently discontinued during CHC treatment (A2)
- A3: Permanently discontinued prior to CHC treatment (A3)
- B: Discontiuned prior to CHC treatment and reinduced post-treatment (B)
- C1 Drug A: Permanently replaced at start of CHC treatment (C1A)
- C1 Drug B: Substitute at start of CHC treatment and discontinued during CHC treatment (C1B)
- C2 Drug A: Permanently replaced at start of CHC treatment (C2A)
- C2 Drug B: Substitute at start of CHC treatment and continued (C2B)
- C3 Drug A: Replaced during CHC treatment (C3A)
- C3 Drug B: Substitute during CHC treatment (C3B)
- D: Introduced during CHC treatment (D)
- No profile reported: No profile reported

Another table will show the associated treatment profiles for the medications of special interest. Therefore the medication will be pooled appropriately. All treatment profiles will be considered.

A further table will show the associated treated conditions, i.e.:

- Alcoholic liver disease
- Angina pectoris
- Auto-immune hepatitis
- Auto-immune skin disease
- · Bipolar disorder
- Chronic kidney disease
- Cryoglobulinemia
- Depression
- Diabetes mellitus (Type 1)

- Diabetes mellitus (Type 2)
- Hemophilia
- Hepatitis B
- Hepatocellular carcinoma
- HIV
- Hypertension
- Hyperthyroidism
- Hypothyroidism
- Immunologically mediated disease
- Insulin resistance
- Kidney transplantation
- Lipid disorder
- Liver transplantation
- Metabolic syndrome
- Myocardial infarction
- Opiate substitution
- Personality disorder
- Porphyria cutanea tarda (PCT)
- Primary biliary cirrhosis
- Schistosomiasis
- Schizophrenia
- Sickle cell anemia
- Steatosis (non-alcoholic)
- Stroke
- Thalassemia
- Tuberculosis
- v. Willebrand disease
- Wilson disease
- Other

All treatment profiles will be considered.

A glossary will show the verbatim terms and the corresponding coded terms used (see Table 12).

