The ABBVIE REGIMEN has been studied with and without RBV in over 2,300 patients in Phase III trials across a variety of patient populations including those with compensated cirrhosis. Based on Phase III data, the ABBVIE REGIMEN, with or without RBV, was well tolerated with a low discontinuation rate. Adverse events (AEs) were typically mild, and many of the AEs and laboratory abnormalities reported were attributable to the presence of RBV. However, these AEs were much milder than observed when RBV was given in combination with interferon. Transient, asymptomatic serum alanine aminotransferase (ALT) elevations were observed at a low rate, were not associated with hepatic dysfunction and generally resolved with ongoing treatment. A disproportionate number of the cases were in women on concurrent ethinyl estradiol-containing therapy (i.e., contraceptives or hormone replacement) and discontinuation of the hormonal therapy with continuation or brief interruption of the ABBVIE REGIMEN led to resolution in serum ALT elevation. Transient elevations in serum bilirubin (predominantly indirect) were observed in subjects receiving the ABBVIE REGIMEN with RBV, related to the inhibition of the bilirubin transporters, organic anion-transporting polypeptides (OATPs) 1B1/1B3, by paritaprevir and RBV-induced hemolysis. Bilirubin elevations occurred after initiation of treatment, peaked by study Week 1, and generally resolved with ongoing therapy. Bilirubin elevations were not associated with aminotransferase elevations. The frequency of indirect bilirubin elevations was lower among subjects who did not receive RBV.

Response of CHC genotype 4 was assessed in the phase II study PEARL-I in which 86 treatment-naïve patients were randomized to the 2 DAA combination of Paritaprevir/r – ombitasvir with vs. without RBV for 12 weeks. The SVR was 100% with RBV vs. 91% without RBV [61]. No serious SAEs or AEs leading to discontinuation were reported.

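### The by-class co-medication table (SAP 4.2.8.2) is limited to drugs taken during treatment, but its profile list omits drugs replaced during treatment (C3 Drug A), so it undercounts on-treatment co-medication

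*SAP*

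**What the plan says.** SAP 4.2.8.2 (Co-medication) plans several frequency tables for the safety population, by treatment regimen and cirrhosis status. The first groups preferred terms by class. It has a stated criterion and a closed list that puts the criterion into practice: "received during treatment specified by ABBVIE regimen will be displayed (Treatment profiles: A1, A2, C1 Drug B, C2 Drug B, C3 Drug B, D".

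The same section then defines the profiles. Those that matter here are:

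- "A2: Permanently discontinued during CHC treatment (A2", which is on the list
- "C1 Drug A: Permanently replaced at start of CHC treatment (C1A" and "C2 Drug A: Permanently replaced at start of CHC treatment (C2A", neither of which is on the list
- "C3 Drug A: Replaced during CHC treatment (C3A", which is not on the list
- "C3 Drug B: Substitute during CHC treatment (C3B", which is on the list

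For the second table the SAP says: "In another table, the co-medication (preferred term) will be grouped by profile. All treatment profiles will be considered". The tables for medications of special interest and for associated treated conditions also take in every profile. In SAP Table 12 the by-class output is `tcom_<c>_tc_sp`.

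**The concern.** The criterion and the list disagree. A drug that is replaced part-way through treatment was being taken with the regimen up to the switch, so it was received during treatment. The list nevertheless keeps only the substitute and drops the drug it replaced.

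How a drug is counted then depends on something unrelated to exposure. If it is stopped mid-treatment and nothing takes its place, it is profile A2 and is counted. If the same drug is stopped at the same time and something takes its place, it is C3 Drug A and is not counted.

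Information on concomitant medication in the Polish population is secondary objective 5 in both documents. The by-class table is the one output that the SAP restricts to on-treatment co-medication. A reader will take its frequencies as complete for that period, and as written they are not.

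**Working it through.** There is no stated figure to reproduce. The check is to test each profile in SAP 4.2.8.2 against the table's criterion (taken during treatment) and then against the list.

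| Profile | Meaning, from the SAP definitions | Taken during treatment? | Listed? |
|---|---|---|---|
| A1 | continued | yes | yes |
| A2 | stopped for good during treatment | yes | yes |
| A3 | stopped for good before treatment | no | no |
| B | stopped before, resumed after treatment | no | no |
| C1 Drug A | replaced at treatment start | no | no |
| C1 Drug B | substitute from the start, stopped during treatment | yes | yes |
| C2 Drug A | replaced at treatment start | no | no |
| C2 Drug B | substitute from the start, continued | yes | yes |
| **C3 Drug A** | **replaced during treatment** | **yes** | **no** |
| C3 Drug B | substitute brought in during treatment | yes | yes |
| D | introduced during treatment | yes | yes |

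Result: 11 named profiles, of which 7 meet the criterion and 4 do not. The list holds 6, all among the 7. 7 − 6 = 1 mismatch, and it is C3 Drug A. The residual category for records without a profile cannot be classified from its definition; it is not listed either.

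Two comparisons within the section suggest an oversight:

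1. Stopping part-way is not a ground for exclusion, because A2 and C1 Drug B both stop during treatment and both are listed.
2. Being the replaced member of a pair is not by itself a ground either. C1 Drug A and C2 Drug A fail the criterion because they are replaced at the start. The SAP words C3 Drug A differently, as replaced during treatment, but the list leaves out all three Drug A profiles alike.

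Effect on the counts, for one patient with a C3 pair (Drug A replaced by Drug B) and no other record of either preferred term or class, assuming each patient counts once per preferred term and once per class:

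| Row of the table | As written | With C3 Drug A added |
|---|---|---|
| Preferred term of Drug A | 0 | 1 |
| Preferred term of Drug B | 1 | 1 |
| Class, if A and B share it | 1 | 1 |
| Class of A, if B is in another class | 0 | 1 |

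The undercount for a preferred term is thus the number of patients whose only on-treatment record of that term is C3 Drug A. For a class, it is the number whose only on-treatment record in that class is C3 Drug A. Neither document gives a frequency for this profile, so these numbers could be zero or more.

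**The case against.** The strongest reply is that nothing leaves the report. Three further tables, in the same population and strata, take in every profile. The by-profile table shows each C3 Drug A preferred term and labels it as replaced during treatment. That is true, and it limits the consequence. It does not correct the by-class table, whose frequencies still contradict its own criterion.

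A second reply is that when both drugs share a class, the class frequency may not change. That also stands, if patients are counted once per class. The preferred-term row for the replaced drug is still short.

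A third is that the table shells in Part II of the SAP are not available here and might carry a scope note. That cannot be checked; the SAP text itself gives no reason for the exclusion.

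A reader might also infer that the missing drugs are the co-exposures most likely to reflect a drug interaction. The documents do not support this. SAP 4.2.8.2 attaches no reason for change to any profile, and under the interaction screening in protocol 9.4.1.5 a change could equally be recorded as A2, A3, B or a replacement at treatment start. Protocol 7.1 might seem to supply an example, since it says of the ALT elevations: "A disproportionate number of the cases were in women on concurrent ethinyl estradiol-containing therapy". But it goes on to describe the hormonal therapy being discontinued and does not mention a substitute. A drug stopped during treatment without one is profile A2, which the table includes.

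**Conclusion.** The point holds as an internal inconsistency in one descriptive table. Followed as written, `tcom_<c>_tc_sp` omits one of the seven profiles that meet its criterion. It undercounts on-treatment co-medication by preferred term, and by class where the substitute is in a different class. The size is unknown because no C3 Drug A count is given.

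The reach is modest. The same records appear in the three all-profile tables, data collection for secondary objective 5 is unaffected, and SVR12 and the other effectiveness results are untouched.

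The conclusion rests on two assumptions. The first is that the treatment period named in the profile definitions is the one meant in the table's criterion; the listing of A2, C1 Drug B, C3 Drug B and D depends on the same reading. The second, which matters only for the class-level effect, is that a patient is counted once per preferred term and once per class; SAP 4.2.8.2 does not state the counting rule.

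**What to change.** In SAP 4.2.8.2, add C3 Drug A to the profile list for the by-class table, and state that each patient is counted once per preferred term and once per class, so that a same-class switch does not count twice in the class row. If leaving the profile out was intended, give the reason and footnote the table so that its frequencies are not read as all on-treatment co-medication. The same sentence should say how records without a profile are handled, since adding C3 Drug A does not settle those.

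The cost is one code in a filter and a line of text. The data are already collected and already feed the other co-medication tables.

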#### 4.2.8.3 Adverse Events

All tolerability variables will be summarized using descriptive statistical methods for the SP stratified by treatment regimen and cirrhosis status and overall.

AEs will be coded using MedDRA. A glossary will show the verbatim terms and the corresponding coded terms used (see Table 12).

The number and percentage of patients with treatment-emergent AEs (i.e. any reported event that begins or worsens in severity after initiation of study drug through 30 days post-study drug dosing including those who are related to the study drug independent of the occurrence and those where the date of onset is missing) will be tabulated by primary MedDRA SOC and PT.

Corresponding summary tables will be provided for all serious treatment-emergent AEs and additional for all non-serious treatment-emergent AEs. In the table of non-serious AEs (that must exclude any SAE) only preferred terms that occurred at a frequency of >=5% in any treatment group will be displayed (no SOCs will be displayed).

The tabulation of the number of patients with treatment-emergent AEs by severity (AEs by severity [mild, moderate, severe], AEs leading to death, AEs leading to hospitalization) and relationship to study drug will also be provided (ABBVIE Regimen, ribavirin, medication error – paritaprevir/r-ombitasvir, medication error – dasabuvir, ABBVIE Regimen withdrawn, ribavirin withdrawn).

Patients reporting more than one AE for a given MedDRA PT will be counted only once for that term using the most severe incident for the severity summary table and the most related for the relationship summary table. Patients reporting more than one type of event within a SOC will be counted only once for that SOC.

The frequency of pregnancies will be displayed as well.

#### 4.2.8.4 Laboratory Data

All reported clinical laboratory test results will be assigned to one of the time points using the time windows specified in the Table 4. All will be performed for the SP by treatment regimen and cirrhosis status.

Changes from baseline to each post-baseline visit will be summarized descriptively (N, mean, SD, median, minimum, maximum). A summary table will show laboratory hematology. In another table, information about clinical chemistry will be summarized.

In a further table CD4 and HIV-RNA are displayed for patients with HIV only by visit.

Instead of the shift tables mentioned in the study protocol, the number and percentage of subjects with post-baseline values until EoT meeting the specified criteria for Potentially Clinically Significant (PCS) laboratory values (defined in Table 10) will be summarized. A post-baseline value must be more extreme than the baseline value to be considered a PCS finding.

Table 10 Criteria for PCS laboratory values

Laboratory data	Very Low	Very High
Laboratory hematology		
Hemoglobin [g/L]	<80	
Platelets [10  /L]	<50	
Laboratory clinical chemistry		
ALT		>5 x ULN and >= 2 x baseline
AST		>5 x ULN and >= 2 x baseline
Creatinine [µmol/L]		>132.605
Creatinine clearance [mL/min]***	<50	

\*\*\* estimated by Cockcroft-Gault-Formula (see above)

Additionally, for hemoglobin and creatinine clearance, the number and percentage of subjects with a maximum Common Terminology Criteria for Adverse Events (CTCAE) Grade of 0, 1, 2, 3, or 4 (see definitions in Table 11) at any post-baseline visit (regardless of the baseline value) through the end of treatment (i.e., Final Treatment Value) will be summarized. For the liver function tests (LFTs) of ALT and AST, the number and percentage of subjects in with a maximum CTCAE Grade of 0, 1, 2, 3, or 4 (see definitions in Table 11) at any post-nadir visit through the end of treatment (i.e., Final Treatment Value) will be summarized. Note, for these analyses, the nadir is used for reference (including baseline).

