9.7.4 Clinical Laboratory Data

All reported clinical laboratory test results will be assigned to one of the time points using the time windows specified in the table below.

Table 4 - Analysis Time Windows

Phase	Time point	Time Window
Pre-Treatment	Baseline	Last value prior to start of study treatment (i.e. ≤study day 1)
Treatment Weeks	4 (day 29)	Study day during treatment period (Study day 1 = first treatment day) 15 - 42
	8 (day 57)	43 - 70
	12 (day 85)	71 - 98
	16 (day 113)	99 - 126
EoT	Actual EoT	Study day of last dose (28 days prior to EoT - 14 days post EoT)
Post Treatment	4 weeks (day 29 post EoT)	15 – 56 post EoT
	12 weeks (day 85 post EoT)	57 – 112 post EoT
	24 weeks (day 169 post EoT)	141 – 196 post EoT

Mean changes from baseline to each post-baseline visit will be summarized descriptively.

Laboratory data values collected during the treatment period will be categorized as low, normal, or high based on reference ranges used in this study. The number and percent of patients who experience post-baseline shifts during treatment in clinical laboratory values from low/normal to high and high/normal to low based on the reference range will be summarized.

Confidential Information

No use or disclose outside AbbVie is permitted without prior written authorization from AbbVie

Additional details of the analyses of clinical laboratory data will be specified in the SAP.

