# 3. STUDY DESIGN

# 3.1 Overview of Study Design and Dosing Regimen

This is a prospective, multi-center observational study in adult patients chronically infected with HCV receiving the interferon-free ABBVIE REGIMEN ± RBV.

University centers and outpatient clinics qualified by training and experience in the management of patients with CHC participate in this study.

The prescription of a treatment regimen is at the discretion of the physician in accordance with local clinical practice and label, is made independently from this observational study and precedes the decision to offer the patient the opportunity to participate in this study.

After written patient authorization has been obtained, patient data including demographic data, HCV disease characteristics, co-morbidities, co-medication, treatment details, and laboratory assessments as recorded in the patient's medical records (source documentation) are documented in the electronic case report form (eCRF). Patients are observed for the duration of the ABBVIE REGIMEN therapy and for up to 24 weeks after treatment completion.

[figure not shown]
The observational period for patients receiving 12 weeks of ABBVIE REGIMEN is max. 36 weeks (12 weeks treatment and 24 weeks post-treatment observation) and for patients receiving 24 weeks of ABBVIE REGIMEN the observational period is max. 48 weeks (24 weeks treatment and 24 weeks post-treatment observation).

Follow-up visits, treatment, procedures and diagnostic methods follow physicians' routine clinical practice. The observational study period entails the following data collection schemes, data documented are those closest to the time windows as indicated in Figure 1:

- 12-week treatment regimen: four visits plus two interim data collection windows
- 24-week treatment regimen: four visits plus three interim data collection windows

This schedule is based on the anticipated regular follow-up for patients undergoing treatment for CHC.

Figure 1 - Study Flowchart

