#### Other co-morbidities

- Kidney transplant
- Chronic kidney disease (Mild, Moderate, Severe, Currently on dialysis, Currently not on dialysis)
- Psychiatric disorders (Depression, Bipolar disorder, Schizophrenia, Personality disorder)
- Diabetes mellitus (Type 1, Type 2)
- o Insulin resistance
- Metabolic syndrome
- Lipid disorder
- o Hyperthyroidism
- Hypothyroidism
- Cardiovascular disease (Myocardial infarction, Angina pectoris, Hypertension, Stroke)
- Immunologically mediated disease
- o Hemophilia
- o Thalassemia
- o Sickle cell anemia
- o V. Willebrand disease
- Psychoactive substance dependency (Active injection drug use, Inhalate cocaine, Marihuana/ cannabis, Opiate substitution)
- o Other

The patient's alcohol consumption will be displayed in a further table, i.e.:

- Alcohol use (None, Yes occasional, Yes regular, Ex-drinker [6 units/drinks per day, none in the last 3 months])
- Average number of units/drinks per week (if regular alcohol use is reported)

One unit/drink is defined as 10 milliliters (or approximately 8 grams) of pure alcohol and equals: 200 ml of beer or 100 ml of wine or 20 ml of hard liquor. An overview of Tables and Listings for the above mentioned variables is given in Table 7.

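### The PCS laboratory count can include patients already past the limit before treatment who have not really changed, so the table should be split by baseline status

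*SAP*

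**What the plan says.** SAP 4.2.8.4 (Laboratory Data) drops the shift tables of Protocol 9.7.4 and summarises instead "the number and percentage of subjects with post-baseline values until EoT meeting the specified criteria for Potentially Clinically Significant (PCS) laboratory values". Table 10 sets the limits: hemoglobin below 80 g/L, platelets below 50, creatinine above 132.605 µmol/L, creatinine clearance below 50 mL/min. The one baseline condition for these four tests is "A post-baseline value must be more extreme than the baseline value to be considered a PCS finding". ALT and AST, in the same table, carry a stricter condition: ">5 x ULN and >= 2 x baseline".

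The protocol's shift tables would have counted patients moving "from low/normal to high and high/normal to low based on the reference range will be summarized". A patient who was already low could not shift to low.

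Neither Protocol 9.2.1 nor the Target Population in SAP 4.2.1 sets a laboratory limit for entry. The baseline summaries provide for cirrhosis and Child-Pugh scores up to 15 (SAP 4.2.6.2), and the co-morbidity list provides for "Chronic kidney disease (Mild, Moderate, Severe, Currently on dialysis, Currently not on dialysis".

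**The concern.** A patient on the normal side of a limit at baseline who later passes it is necessarily more extreme than at baseline. The more-extreme condition therefore does no work for that patient. It operates only for patients already past the limit, and for them it is the only filter: any worsening, however small, in any one value is enough. The sponsor set a minimum change for ALT and AST but not for the other four tests.

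The PCS table is produced for the safety population by treatment regimen and cirrhosis status. If patients already past a limit are unevenly spread over those strata, or are tested more often in some of them, the PCS percentages will differ between strata without any difference in what happened on treatment. Tolerability is a stated secondary objective, and the table does not let a reader separate the two sources.

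**Working it through.** The documents give no PCS rate, within-patient variation or baseline prevalence, so there is no plan figure to reproduce.

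**Inputs from the documents.** The Table 10 limits, the more-extreme rule, and the sufficiency of one value are given above. The number of on-treatment values, k, is not stated. SAP 3.1 describes "12-week treatment regimen: four visits plus two interim data collection windows". Set against the columns of SAP Table 2, this reads as about two on-treatment values for 12 weeks (on-treatment and EoT) and three for 24 weeks. The windows in SAP Table 4 (weeks 4, 8, 12, 16 and EoT) would allow about three to five. Only routine-care data are collected, so k may be 0 or 1 for some patients.

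**Assumed inputs.** Log-normal true values and log-normal within-patient noise. The medians, log-SDs and CVs are assumptions.

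**Step 1, closed form.** For a patient well past the limit with no true change and no ties, baseline is equally likely to take any rank among the k+1 values. The chance that at least one later value is more extreme is k/(k+1): 1/2 = 50%, 2/3 = 67%, 3/4 = 75%, 5/6 = 83% for k = 1, 2, 3, 5. This is a ceiling. It ignores ties, and it ignores the fact that patients selected on a measured baseline past the limit tend to drift back.

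**Step 2, simulation with no true change.** Patients are selected because the measured baseline is past the limit. Platelets and creatinine are rounded to whole units and clearance to 0.1. A patient is counted if any of k values is past the limit and strictly more extreme than baseline.

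| Assumption (median / log-SD) | CV | Past limit at baseline | k=1 | k=2 | k=3 | k=5 |
|---|---|---|---|---|---|---|
| Platelets 110 / 0.45 | 5% | 3.9% | 36.5% | 51.9% | 60.7% | 70.9% |
| Platelets 110 / 0.45 | 10% | 4.2% | 33.6% | 49.3% | 58.2% | 68.1% |
| Platelets 110 / 0.45 | 15% | 4.6% | 29.2% | 44.2% | 53.5% | 63.7% |
| Creatinine 75 / 0.30 | 10% | 3.6% | 29.8% | 44.3% | 53.7% | 64.3% |
| Clearance 95 / 0.40 | 10% | 6.0% | 36.4% | 52.1% | 61.1% | 71.2% |

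Across assumptions of this kind with CV 5-15%, the ranges are 25-41% (k=1), 38-58% (k=2), 48-67% (k=3) and 57-75% (k=5). A wider set, with CVs down to 4% and with limits that very few patients exceed at baseline, gives 16-44%, 26-60%, 32-69% and 44-78%. Hemoglobin was not simulated; the rule is the same.

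**Step 3, share of all no-effect PCS cases already past the limit.** For platelets 110 / 0.45, CV 10%, k=3, the baseline-positive cases are 0.0418 × 0.582 = 0.0243 of all patients. The no-effect PCS rate over all patients is 0.0458, so the share is 0.0243 / 0.0458 = 53%. With k = 3-5, platelets 130 / 0.45 give 65-68% at CV 5%, 45-47% at CV 10% and 34-35% at CV 15%. Clearance 90 / 0.35 gives 65-68%, 46-48% and 34-36%. Over all assumptions tried, the share is roughly 30-75%.

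**Step 4, sensitivity to true improvement.** If platelets truly rise on treatment (110 / 0.45, CV 10%, k=3), the 58% falls to 43% for a 5% rise, 29% for 10% and 11% for 20%.

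**Step 5, linked findings.** Clearance is computed from creatinine by the Cockcroft-Gault formula (SAP 4.2.6.5), so one high creatinine reading can produce two PCS findings.

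**The case against.** Requiring worsening from baseline is a common treatment-emergent convention, and it keeps true deterioration in already abnormal patients in the count. The protocol's shift rule had no minimum change or confirmation either. Baseline context is also planned: platelets, creatinine and graded clearance at baseline are tabulated for the safety population by the same strata (SAP 4.2.6.5 and Table 7), Table 11 grades the worst on-treatment clearance, and changes from baseline are summarised by visit. The PCS table is descriptive. Its layout is in Part II of the SAP, which is not among the documents and may already separate patients by baseline status.

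Much of this stands. What remains is that stratum-level baseline tables do not say which PCS cases pre-existed. The CTCAE summary for hemoglobin and clearance disregards the baseline value by design, and Table 11 omits platelets and creatinine.

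A reader might infer more: that most patients past a limit will be counted, or that the PCS percentages will largely reflect pre-existing disease. The documents do not support either. The first fails with one value, is about even with two, and fails if values improve. The second depends on the CV: at 10-15% the majority of no-effect cases in several scenarios are new crossings by patients just inside the limit. Nor do the documents show that dialysis patients are enrolled. The co-morbidity list shows only that the category is recorded, and treatment must follow a local label that is not reproduced. No reason appears why the ribavirin groups in particular would be affected.

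**Conclusion.** The point holds in a limited form. For hemoglobin, platelets, creatinine and creatinine clearance, the rule can count a patient already past the limit before treatment without real change. Under no true change this happens often: around half the time at the two to three values that the schedule suggests, and less with one value. The PCS table by regimen and cirrhosis status therefore mixes pre-existing abnormality with on-treatment change, in proportions that the documents do not allow anyone to fix in advance. All rates rest on assumed k, CV and baseline distributions. The effect is confined to a descriptive safety table and does not touch SVR12. Separating the two groups is a cheap improvement rather than the repair of a primary analysis.

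**What to change.** In SAP 4.2.8.4 and the shell for tpcs_<c>_tc_sp, split hemoglobin, platelets, creatinine and creatinine clearance by baseline status:

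- **Row (a), newly occurring PCS:** patients whose baseline value did not meet the criterion, with those patients as the denominator.
- **Row (b), criterion already met at baseline:** patients whose baseline value met it, reported with their own denominator under the existing more-extreme rule.

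Leave the ALT and AST criteria as they are. If the Part II shells already make this split, only the SAP text needs to say so.

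The cost is SAP wording and one extra row per parameter, from data already collected. The main count would no longer include true worsening in patients abnormal at baseline, but they stay visible in row (b). The split does not remove noise crossings by patients just inside the limit. A minimum relative change in row (b) would filter more noise, but the documents offer no figure for it, so it is not proposed here.
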